If the microbiological surveillance in a few sentinel sites (see chapter 8.3) identifies a dengue outbreak, a dengue rapid test will be added to the "unspecific fever" branch of the algorithm and tested using the same study design as above. The modified "unspecific fever" branch including dengue testing will be implemented in all children if the clinical cure rate with this new branch is better (i.e. >30% decrease in the clinical failure rate) than that of children managed with the original "unspecific fever" branch will revert to the original version and the use of dengue rapid tests will be stopped.

Assessing the utility of typhoid rapid tests in high prevalence conditions:

If the prevalence of typhoid in febrile children is shown to be >10% in a certain area or time period (based on the microbiological surveillance data), using rapid tests, even with sub-optimal sensitivity and specificity as it is the case for now, could be beneficial from a clinical point of view. Indeed, with a pre-test probability of 10% and a positive likelihood ratio of 4 for the typhoid RDT, the post-test probability is 30%. The performance of the test can be enhanced by adding clinical predictors identified in previous studies in Tanzania (De Santis et al. 2017).

In this situation, a typhoid rapid test will be added to the "unspecific fever" branch of the algorithm and its clinical utility assessed using the same design as above. The new "unspecific fever" branch including the typhoid rapid test would be implemented in all children of the high prevalence area, if the clinical cure rate with the new branch is better (i.e. >30% decrease in the clinical failure rate) than that of the original branch. When typhoid prevalence decreases, the "unspecific fever" branch will revert to its original version.

Improving prediction of a severe clinical outcome:

If a combination of demographic, clinical and/or laboratory predictors, or a new POC test, seems to allow for better identification of children who will develop severe disease and thus be hospitalized secondarily or die, the benefit of adding an alert to HCWs in the algorithm, recommending them to refer the child to hospital, will be evaluated. If adding this alert allows to decrease mortality by at least 10%, it will be implemented for all children.

Adapting the algorithm to improve cure rates of children with chronic disease risk factors:

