Since the intervention takes place at the health provider level and their practices are influenced by the context of the health facility they are working in, randomization at health facility level rather than at HCW level or at individual patient level was chosen. The randomization of clusters (i.e. health facilities) will be performed on a 1:1 ratio. Thus, ePOCT+ will be provided to health care workers of 20 of the 40 selected primary health care facilities (intervention arm) in the Morogoro and Mbeya regions, while the other 20 health facilities (HFs) will serve as controls (control arm). Sick children aged 1 day to 14 years (inclusive) will be managed in accordance with the study arm to which the HF they attend has been assigned. The comparator for Phase 1 will be routine care as currently implemented in Tanzania supplemented with equivalent clinical training given to the intervention arm. This includes routine clinical supervision visits performed by CHMT members. To assess the primary and secondary outcomes, final decision on referral, laboratory test results, diagnoses and treatments at initial consultation will be recorded by HCWs electronically in both arms (in the intervention arm integrated into the CDSA; in the control arm via a simple eCRF without any decision support); children will also be followed-up by a phone call or home visit to their caregiver at day 7 (range 6-14) to determine their clinical status. The study is considered as pragmatic since there are no major exclusion criteria to the population of interest, and the setting and organization of the health facilities remains mostly the same (see PRECIS-2 wheel below).

The trial design is summarized below:

PRECIS-2 (Pragmatic-Explanatory Continuum Indicator Summary 2) wheel summarizing the extent of pragmatism of the study:

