## 3.3 Sample size

The primary analysis will evaluate whether the use of ePOCT+ for case management of sick children in PHC facilities 1) results in similar clinical cure at day 7 (non-inferiority analysis), as compared to routine care and 2) decreased antibiotic prescriptions (superiority analysis) at the initial consultation. The sample size was calculated for testing the non-inferiority of the clinical cure outcome, which will require a much larger sample size due to the rareness of clinical failure. In addition, the testing of differences in antibiotic prescription is conditional on satisfying non-inferiority in the clinical outcome. Assuming a failure rate (not being cured at day 7) of 3% in the control arm (corresponding to a 97% clinical cure rate), based on previous studies, the acceptable non-inferiority margin will be a risk ratio of 1.3. This corresponds to the upper bound of the difference in failure rate not exceeding 0.9% if the control group failure rate is 3%. We utilized a fixed risk ratio rather than an absolute risk difference to protect against potential unexpected event rates (Head et al. 2012).

We assumed a cluster size of 900 patients (average of 150 patients per month x 6 months) and an intraclass correlation coefficient of 0.002 in the clinical outcome based on similar studies. To have 80% power to detect a risk ratio 1.3, for a one-sided hypothesis test at alpha of 0.025, we would require 19 clusters and 17,100 patients per arm (total patients n=37,620 assuming 10% loss to follow-up), rounded to a total of 40 HFs and 40,000 patients. However, due to uncertainty regarding the assumptions of the sample size calculation and to capture a wider more representative range of conditions, we will continue recruitment for Phase 1 for a minimum of 6 months.

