Analysis: Compare change in percentage of prescription from month to month, and from first half of the study compared to second half of the study for the intervention arm and the control arm, using the control arm as comparison to correct for seasonality, and presenting implementation team mentorship visits and combined implementation team and CHMT mentorship visits to contextualize changes. Independent sample t-test will be used to compare change in antibiotic prescription between intervention and control arm.

- Change in % of children with basic anthropometrics and clinical signs assessed (intervention arm only)

Timing and method of measurement: Measurement and documentation of individual basic measurements (height, MUAC, Temperature), and clinical signs (respiratory rate) as documented within the ePOCT+ tool during the initial assessment (Day 0).

Analysis: Descriptive statistics presenting change in documentation of basic measurements and clinical signs from month to month, and from first half of the study compared to second half of the study. Dates of implementation team mentorship visits and combined/supervised implementation team and CHMT mentorship visits and any changes in implementation strategy will also be presented to contextualize the changes. Subgroup analyses may be conducted for each intervention health facility.

- Change in % of cases managed using ePOCT+ over time (intervention arm only):

Timing and method of measurement: Uptake of ePOCT+ is defined as the use of the ePOCT+ tool to guide the clinical consultation including the decision on what treatment to prescribe during the initial consultation (Day 0).

Analysis: Descriptive statistics to present change in the proportion of health care workers' uptake from month to month, and from first half of the study compared to second half of the study will be presented. Dates of implementation team mentorship visits and combined/supervised implementation team and CHMT mentorship visits and any changes in implementation strategy will also be presented to contextualize the changes. Subgroup analyses may be conducted for each intervention health facility.

- Prognostic value of individual or combined predictors during the initial consultation to predict clinical failure/cure, hospitalization for more than one night and mortality (intervention arm)

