Timing and method of measurement: Individual or combined predictors as documented in the eCRF during the initial consultation in the intervention arm. Clinical failure, hospitalization more than one night, and mortality assessed during the phone calls or home visit at day 7.

Method of analysis: ORs and 95% confidence intervals will be calculated using Pearson's chi-squared test or Fisher's exact test (two-tailed) for binary individual predictors. Initial selection of individual

predictors for the bivariate models will be determined by a group of clinical experts, with consideration of the algorithmic logic of the intervention tool to avoid circularity, and evidence on predictors already found to be prognostic. Multivariable ordinal logistic regression with lasso penalty will be used for covariate selection of the final model. Validity tests will be calculated including sensitivity, specificity, positive likelihood ratio, negative likelihood ratio, and area under the receiver operating characteristic. The dataset will be divided into a portion used for the derivation, and another portion for validation.

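### SAP 6.3 validates the exploratory prognostic model on one unspecified split of the intervention arm, which costs precision that full-data internal validation would keep

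*SAP*

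**What the plan says.** The last item of SAP 6.3 (Exploratory analyses) is: "Prognostic value of individual or combined predictors during the initial consultation to predict clinical failure/cure, hospitalization for more than one night and mortality". It is restricted to the intervention arm. Clinical experts preselect the predictors, taking account of the algorithm's logic and of published evidence. For the model itself, "Multivariable ordinal logistic regression with lasso penalty will be used for covariate selection of the final model". Performance is summarized by sensitivity, specificity, the two likelihood ratios and the area under the ROC curve. Validation is covered in one sentence: "The dataset will be divided into a portion used for the derivation, and another portion for validation".

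The SAP does not give the size of either portion, whether the division is by child, facility or calendar time, the expected number of events for each outcome, or any resampling or calibration step.

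On later use, Protocol 10.4.1 lists better identification of children who had severe outcomes in Phase 1 among the aims of algorithm modification. Protocol 8.2 considers a referral alert if a set of predictors "seems to allow for better identification of children who will develop severe disease".

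**The concern.** A single split uses the events inefficiently: the lasso chooses predictors from one part, and the accuracy figures come from the other. When outcomes are rare, selection becomes less stable and the accuracy intervals become wider than the data require. Resampling methods use every event for both purposes and correct for overfitting.

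The unstated unit also matters. SAP 3.1 randomizes facilities because practice depends on facility context, and Protocol 3.2 extends the tool to as many as 60 additional facilities. A reader of the results will want to know whether performance carries over to facilities that did not contribute to the model, and the current text does not guarantee an answer.

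The stake is modest. The analysis is exploratory and bears on no primary or secondary result. What it could do is give misleading support to, or wrongly discard, candidate predictors that clinicians later consider.

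**Working it through.** **1. Number of analysable children.** SAP 3.3 assumes 3% failure, a margin of 0.9 percentage points, 80% power, one-sided alpha 0.025, 900 per cluster and ICC 0.002.

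- Individual randomization: (1.960 + 0.842)² × 2 × 0.03 × 0.97 / 0.009² ≈ 5,640 per arm.
- Design effect: 1 + 899 × 0.002 = 2.798, giving about 15,780 per arm, or 15,780 / 900 = 17.5 clusters.
- With a t reference on 2(k − 1) degrees of freedom, power is 78.7% at 18 clusters and 81.0% at 19. So 19 × 900 = 17,100, which reproduces the plan: "we would require 19 clusters and 17,100 patients per arm (total patients n=37,620 assuming 10% loss to follow-up".
- 2 × 17,100 × 1.10 = 37,620. Loss to follow-up is added on top, so 900 per cluster is already the analysable size and no further 10% should be removed. The base is 17,100.

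**2. Clinical failures.** The SAP's figure is for controls: "Assuming a failure rate (not being cured at day 7) of 3% in the control arm". Taking the same rate in the intervention arm (an assumption), 17,100 × 0.03 = 513.

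**3. Deaths.** The documents give no day-7 death rate. Assumed range: 0.05% to 0.3%, so 17,100 × 0.0005 = 8.6 to 17,100 × 0.003 = 51.3 deaths in the whole arm. The validation share is also not given. Assumed range: one third to one half.

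**4. Precision of an AUROC of 0.80 (Hanley–McNeil).** With n₁ events and n₀ non-events,

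SE² = [A(1 − A) + (n₁ − 1)(a − A²) + (n₀ − 1)(b − A²)] / (n₁n₀), where a = A/(2 − A) and b = 2A²/(1 + A).

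At A = 0.80, a − A² = 0.0267 and b − A² = 0.0711. For all 513 failures and 16,587 non-failures, the numerator is 0.16 + 512 × 0.0267 + 16,586 × 0.0711 ≈ 1,193. Dividing by 513 × 16,587 gives SE ≈ 0.0118 and a 95% half-width of 1.96 × 0.0118 ≈ 0.023. The other rows follow in the same way.

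| Outcome | Data used | Events | Half-width |
|---|---|---|---|
| Failure, 3% | all | 513 | 0.023 |
| Failure, 3% | one half | 257 | 0.033 |
| Failure, 3% | one third | 171 | 0.040 |
| Death, 0.05% (assumed) | all | 8.6 | 0.18 |
| Death, 0.05% | one half | 4.3 | 0.25 |
| Death, 0.05% | one third | 2.9 | 0.31 |
| Death, 0.3% (assumed) | all | 51.3 | 0.07 |
| Death, 0.3% | one half | 25.7 | 0.10 |
| Death, 0.3% | one third | 17.1 | 0.13 |

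**5. How far the result depends on the assumed death rate.** Taking 100 validation deaths as an illustrative benchmark, the rate would have to be 100 / 8,550 = 1.2% with a half share or 100 / 5,700 = 1.8% with a third. That equals 39% or 58% of the 3% assumed for all failures. A small number of validation deaths is therefore a robust conclusion, even though the exact count is not.

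**6. Factors that would lower the counts.** SAP 3.4 reports enrollment below expectation, without a number. SAP 6.2 cites earlier phone follow-up losses of 13–25%. With 37,620 / 2 = 18,810 enrolled per arm, those losses leave 16,365 to 14,108 children and 491 to 423 failures. Half-widths would grow by at most √(17,100 / 14,108) ≈ 1.10. Clustering and the selection step widen all intervals further.

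**7. Deaths per facility.** Over 19 clusters the average is 8.6 / 19 = 0.45 to 51.3 / 19 = 2.7. At the low end, a Poisson count gives exp(−0.45) ≈ 64% of facilities with no death, so accuracy within single left-out facilities could not be computed reliably.

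**The case against.** The strongest reply is that the split is a recognized method in an analysis labelled exploratory, that expert preselection and the lasso already restrain overfitting, and that a held-out portion is easy to explain. This is fair. It makes the change an improvement rather than the correction of an error.

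A reader might also infer more than the documents support, in four ways.

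- **That the split makes severe-outcome prediction as a whole unsupportable.** The model is ordinal, and the outcomes include hospitalization for more than one night, for which no expected rate is given. Protocol 8.2 also describes severe disease as leading to secondary hospitalization or death. The imprecision is shown for mortality alone, and clinical failure remains workable on a third of the data.
- **That the split causes the shortage of deaths.** Rarity is the main cause. The unsplit arm would have only about 9 to 51 deaths on the same assumptions.
- **That children from the same facilities would sit in both parts.** That follows only if the split is by child. A split by facility, region or time would fit the SAP's wording equally well. The defect is that the unit is unstated.
- **That Phase 2 would adopt this model's output.** The SAP does not tie the model to Phase 2. Protocol 8.2 puts expert review, retrospective testing and, where feasible, a randomized sub-study before adoption, and requires the severe-outcome alert to be evaluated first. Protocol 12.2 adds that no change is automatic. Whether those evaluations would be large enough is a separate question.

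**Conclusion.** The point holds as a low-cost improvement. A single split of unstated fraction and unit is less precise than internal validation on all the data. For clinical failure, the AUROC half-width rises from about 0.023 to between 0.033 and 0.040, which is a loss but not a fatal one. For deaths it is about 0.31 to 0.10 with a split and 0.18 to 0.07 without, so replacing the split helps but does not make mortality-specific accuracy well estimated.

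The failure figures rest on 17,100 analysable children and on the control-arm rate of 3% applying in the intervention arm. The death figures rest on a death rate and a validation share that the documents do not give, so 3 to 26 validation deaths is an assumed range and not a figure of the plan. The results could inform Phase 2 algorithm changes but do not determine them. No primary or secondary analysis is affected.

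**What to change.** In SAP 6.3, replace the sentence on dividing the dataset with the following:

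- Develop the model on all intervention-arm children with follow-up.
- Report optimism-corrected performance from a bootstrap that resamples facilities and repeats the full lasso selection in each resample.
- Add internal-external validation that leaves out facilities in turn, with predictions pooled across folds before accuracy is computed, because many single facilities could have no deaths.
- State the expected number of events for each outcome, and report mortality-specific accuracy as descriptive only.

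If the sponsor prefers to keep a split, the SAP should fix its fraction and its unit before the data are examined.

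The cost is a change of wording and some computing time, with no additional data. The one real loss is that no single untouched hold-out set remains.
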